12.2.2 Analyses of safety endpoints

Analysis on safety endpoints will be performed for patients who take at least one dose of the trial treatment and for whom post-dose data have been collected. Efficacy endpoints will be analyzed by randomized treatment and safety endpoints will be analyzed by treatment received.

12.2.3 Interim analyses

No interim analysis will be performed for this trial.

12.3 Determination of sample size

The primary objective of this study is to compare the symptom control rate in 8 weeks treatment regimen group, and 2 weeks treatment regimen group after 24 weeks maintenance treatment/ follow-up. Since we do not have previous data for the symptom control rate in the two treatment regimens, the sample size was calculated based on clinical experience. With a total of 170 evaluable patients, 85 in the 8 weeks treatment regimen group and 85 in the 2 weeks treatment regimen group, the power would be over 80% to detect a difference of 20% in symptom control rate between two treatment groups at two-sided 0.05 significance level using Fisher exact test, assuming the symptom control rate is around 66% in 2 weeks treatment regimen group and 86% in 8 weeks treatment regimen group (based on data from BU-NEG-0005 study). Considering the PPI response rate is around 70% and drop off rate will be 20%, around 300 patients are needed to be randomised.

12.4 Data monitoring committee

Not applicable in this study.

13. IMPORTANT MEDICAL PROCEDURES TO BE FOLLOWED BY THE INVESTIGATOR

13.1 Medical emergencies and AstraZeneca contacts

The Principal Investigator is responsible for ensuring that procedures and expertise are available to handle medical emergencies during the study. **A medical emergency usually constitutes an SAE and is to be reported as such, see Section 6.4.4**

In the case of a medical emergency the investigator may contact the Study Delivery Team Leader. If the Study Delivery Team Leader is not available, contact the Study Delivery Team Physician/other physician at the AstraZeneca Research and Development.

Name	Role in the study	Address & telephone number
------	-------------------	----------------------------

13.2 Overdose

Data are limited but single doses of 80 mg esomeprazole oral was uneventful. No specific antidote is known. Esomeprazole is extensively plasma protein bound and is therefore not readily dialyzable. As in any case of overdose, treatment should be symptomatic and general supportive measures should be utilized.

- An overdose with associated AEs is recorded as the AE diagnosis/symptoms on the relevant AE modules in the CRF and on the Overdose CRF module.
- An overdose without associated symptoms is only reported on the Overdose CRF module.

If an overdose on an AstraZeneca study drug occurs in the course of the study, then investigators or other site personnel inform appropriate AstraZeneca representatives **within**

one day, ie, immediately but no later than **the end of the next business day** of when he or she becomes aware of it.

The designated AstraZeneca representative works with the investigator to ensure that all relevant information is provided to the AstraZeneca Patient Safety data entry site.

For overdoses associated with SAE, standard reporting timelines apply, see Section 6.4.4. For other overdoses, reporting should be done within 30 days.

13.3 Pregnancy

All outcomes of pregnancy should be reported to AstraZeneca.

For esomeprazole, limited clinical data on exposed pregnancies are available. Animal studies with esomeprazole do not indicate direct or indirect harmful effects with respect to embryonal/fetal development. Animal studies with the racemic mixture do not indicate direct or indirect harmful effects with respect to pregnancy, parturition, or postnatal development. Caution should be exercised when prescribing to pregnant women. Therefore, women participate in the present study must be either non-pregnant or postmenopausal or using a reliable form of contraception.

13.3.1 Maternal exposure

If a subject becomes pregnant during the course of the study, investigational product should be discontinued immediately.

Pregnancy itself is not regarded as an adverse event unless there is a suspicion that the investigational product under study may have interfered with the effectiveness of a contraceptive medication. Congenital abnormalities/birth defects and spontaneous miscarriages should be reported and handled as SAEs. Elective abortions without complications should not be handled as AEs. The outcome of all pregnancies (spontaneous miscarriage, elective termination, ectopic pregnancy, normal birth or congenital abnormality) should be followed up and documented even if the subject was discontinued from the study.

If any pregnancy occurs in the course of the study, then investigators or other site personnel inform appropriate AstraZeneca representatives **within one day** ie, immediately but no later than the **end of the next business day** of when he or she becomes aware of it.

The designated AstraZeneca representative works with the investigator to ensure that all relevant information is provided to the AstraZeneca Patient Safety data entry site within 1 or 5 days for SAEs, see Section 6.4.4 and within 30 days for all other pregnancies.

The same timelines apply when outcome information is available.

Appendix B
Additional Safety Information

FURTHER GUIDANCE ON THE DEFINITION OF A SERIOUS ADVERSE EVENT (SAE)

Life threatening

‘Life-threatening’ means that the subject was at immediate risk of death from the AE as it occurred or it is suspected that use or continued use of the product would result in the subject’s death. ‘Life-threatening’ does not mean that had an AE occurred in a more severe form it might have caused death (eg, hepatitis that resolved without hepatic failure).

Hospitalisation

Outpatient treatment in an emergency room is not in itself a serious AE, although the reasons for it may be (eg, bronchospasm, laryngeal oedema). Hospital admissions and/or surgical operations planned before or during a study are not considered AEs if the illness or disease existed before the subject was enrolled in the study, provided that it did not deteriorate in an unexpected way during the study.

Important medical event or medical intervention

Medical and scientific judgement should be exercised in deciding whether a case is serious in situations where important medical events may not be immediately life threatening or result in death, hospitalisation, disability or incapacity but may jeopardize the subject or may require medical intervention to prevent one or more outcomes listed in the definition of serious. These should usually be considered as serious.

Simply stopping the suspect drug does not mean that it is an important medical event; medical judgement must be used.

Examples of such events are:

- Angioedema not severe enough to require intubation but requiring iv hydrocortisone treatment
- Hepatotoxicity caused by paracetamol (acetaminophen) overdose requiring treatment with N-acetylcysteine
- Intensive treatment in an emergency room or at home for allergic bronchospasm
- Blood dyscrasias (eg, neutropenia or anaemia requiring blood transfusion, etc) or convulsions that do not result in hospitalisation
- Development of drug dependency or drug abuse.

A GUIDE TO INTERPRETING THE CAUSALITY QUESTION

The following factors should be considered when deciding if there is a “reasonable possibility” that an AE may have been caused by the drug.

- Time Course. Exposure to suspect drug. Has the subject actually received the suspect drug? Did the AE occur in a reasonable temporal relationship to the administration of the suspect drug?
- Consistency with known drug profile. Was the AE consistent with the previous knowledge of the suspect drug (pharmacology and toxicology) or drugs of the same pharmacological class? OR could the AE be anticipated from its pharmacological properties?
- Dechallenge experience. Did the AE resolve or improve on stopping or reducing the dose of the suspect drug?
- No alternative cause. The AE cannot be reasonably explained by another aetiology such as the underlying disease, other drugs, other host or environmental factors.
- Rechallenge experience. Did the AE reoccur if the suspected drug was reintroduced after having been stopped? AstraZeneca would not normally recommend or support a rechallenge.
- Laboratory tests. A specific laboratory investigation (if performed) has confirmed the relationship?

A “reasonable possibility” could be considered to exist for an AE where one or more of these factors exist.

In contrast, there would not be a “reasonable possibility” of causality if none of the above criteria apply or where there is evidence of exposure and a reasonable time course but any dechallenge (if performed) is negative or ambiguous or there is another more likely cause of the AE.

In difficult cases, other factors could be considered such as:

- Is this a recognised feature of overdose of the drug?
- Is there a known mechanism?

Ambiguous cases should be considered as being a “reasonable possibility” of a causal relationship unless further evidence becomes available to refute this. Causal relationship in cases where the disease under study has deteriorated due to lack of effect should be classified as no reasonable possibility.

[figure not shown]
Clinical Study Protocol Appendix C

Drug Substance Esomeprazole

Study Code D9612L00127

Edition Number 1.0

Appendix C
GerdQ

Please answer all the questions below. The answers will assist your doctor in finding the best treatment choice to ensure that your life gets back to normal.

[figure not shown]
Think about *the past seven days...*

Tick only one box per question

A Symptoms differ from person to person

1. **How often** did you have a burning feeling behind your breastbone (heartburn)?
2. **How often** did you have stomach contents (liquid or food) moving upwards to your throat or mouth (regurgitation)?

0 DAYS	1 DAY	2-3 DAYS	4-7 DAYS
0 DAYS	1 DAY	2-3 DAYS	4-7 DAYS

B

1. **How often** did you have a pain in the center of the upper stomach?
2. **How often** did you have nausea?

0 DAYS	1 DAY	2-3 DAYS	4-7 DAYS
0 DAYS	1 DAY	2-3 DAYS	4-7 DAYS

C It is important for your doctor to fully understand how your daily life is affected by your symptoms

1. **How often** did you have difficulty getting a good night's sleep because of your heartburn and/or regurgitation?
2. **How often** did you take additional medication for your heartburn and/or regurgitation other than what the physician told you to take? (such as Tums, Roloids, Maalox?)

0 DAYS	1 DAY	2-3 DAYS	4-7 DAYS
0 DAYS	1 DAY	2-3 DAYS	4-7 DAYS

Please discuss with your doctor any ways GERD impacts your life

Name _____ Date _____

Clinical Study Protocol Amendment

Amendment Number	1
Drug Substance	Esomeprazole
Study Code	D9612L00127
Date	
Protocol Dated	

A multicenter, randomized, open-label Phase IV study exploring symptom control rate in co-diagnosed NERD and chronic gastritis patients treated with 8 weeks esomeprazole treatment regimen and 2 weeks esomeprazole treatment regimen

This submission /document contains trade secrets and confidential commercial information, disclosure of which is prohibited without providing advance notice to AstraZeneca and opportunity to object.

Sponsor:

Astrazeneca China

Centres affected by the Amendment:

This amendment affects all centres in the study.

The protocol for the study is to be amended as follows:

Add “To compare the success rate between 8 weeks esomeprazole treatment regimen group and 2 weeks esomeprazole treatment regimen group in co-diagnosed NERD and chronic gastritis patients” as secondary objective. Secondary variables are updated accordingly, “The success rate in 8 weeks treatment regimen group, compared with 2 weeks treatment regimen group after 24 weeks on-demand maintenance treatment/ follow up. Success is defined as patients who relieved after 8 weeks or 2 weeks esomeprazole treatment, and also get symptom controlled after 24 weeks maintenance treatment/follow up period.” is added.

The number of drug dispensed during 24 weeks on-demand maintenance treatment period is changed from 14 tablets to 28 tablets esomeprazole.

Per Protocol population was differentiated as ITT-PP and MITT-PP, defined as all subjects without significant protocol violations/deviations out of ITT, and MITT population respectively.

Section of protocol affected:

2.2 Secondary objectives

Previous text:

2.2 Secondary objectives

- To assess time to first relapse, defined as the time to the patients first come to see the investigator because of symptom recur, and need for treatment after 8 weeks or 2 weeks esomeprazole treatment in the two treatment regimen groups.
- To assess symptom control rate after 8 /16 weeks visits in 24 weeks maintenance treatment/follow up period, as evaluated by GerdQ.
- To assess the symptom relief rate after 8 weeks or 2 weeks esomeprazole treatment in the two different treatment regimen groups.
- In the 8 weeks treatment regimen group, to compare the symptom relief rate after 2 weeks and 8 weeks treatment.
- To compare the number of unscheduled hospital visit between the two different treatment regimen groups.
- To measure patient satisfaction in the two different treatment regimen groups.

Revised text:

2.2 Secondary objectives

- To compare the success rate between 8 weeks esomeprazole treatment regimen group and 2 weeks esomeprazole treatment regimen group in co-diagnosed NERD and chronic gastritis patients. Success is defined as patients who relieved after 8 weeks or 2 weeks esomeprazole treatment, and also get symptom controlled after 24 weeks maintenance treatment/follow up period.
- To assess time to first relapse, defined as the time to the patients first come to see the investigator because of symptom recur, and need for treatment after 8 weeks or 2 weeks esomeprazole treatment in the two treatment regimen groups.
- To assess symptom control rate after 8 /16 weeks visits in 24 weeks maintenance treatment/follow up period, as evaluated by GerdQ.
- To assess the symptom relief rate after 8 weeks or 2 weeks esomeprazole treatment in the two different treatment regimen groups.

- In the 8 weeks treatment regimen group, to compare the symptom relief rate after 2 weeks and 8 weeks treatment.
- To compare the number of unscheduled hospital visit between the two different treatment regimen groups.
- To measure patient satisfaction in the two different treatment regimen groups.

Reason for Amendment:

Relief rate is to evaluate the efficacy of initial 8 week or 2 week treatment, and symptom control rate is to evaluate the efficacy of 24 weeks maintenance treatment/follow up period. Now success rate is added to evaluate the efficacy of whole treatment regimen, it is the combination of relief and control.

Section of protocol affected:

5.5.2 Doses and treatment regimens

Previous text:

8 weeks treatment regimen group:

During 24 weeks on-demand maintenance treatment period, 14 tablets esomeprazole will be dispensed at each scheduled visit. If it is not enough before next scheduled visit, patients can go to the study center to get extra drugs. If they do not have symptoms recur, and just come to get on-demand drugs, it is not considered as unscheduled visit.

Revised text:

8 weeks treatment regimen group:

During 24 weeks on-demand maintenance treatment period, 28 tablets esomeprazole will be dispensed at each scheduled visit. If it is not enough before next scheduled visit, patients can go to the study center to get extra drugs. If they do not have symptoms recur, and just come to get on-demand drugs, it is not considered as unscheduled visit.

Reason for Amendment:

During study operation, we found some patients in 8 week treatment regimen group did not go to the study center to get extra drugs when their drugs used up. They only went to the study center until their symptom recurred. To ensure these patients have drugs and really with on-demand treatment, we decided to increase the number of drugs dispensed at each scheduled visit.

Persons who initiated the Amendment:

Study physician

Section of protocol affected:

6.3.1 Summary of efficacy objectives and variables

Previous text:

Table 1 Efficacy objective and endpoints relating to objective

Objective	Summary variables for analysis (including timepoint and population)	Statistical analysis methods or presentation of data
Primary Objective	Primary variable	
To compare the symptom control rate between 8 weeks esomeprazole treatment regimen group and 2 weeks esomeprazole treatment regimen group in co-diagnosed NERD and chronic gastritis patients, as evaluated by GerdQ after 24 weeks maintenance treatment/follow up.	The symptom control rate in 8 weeks treatment regimen group, compared with 2 weeks treatment regimen group after 24 weeks on-demand maintenance treatment/ follow up. Controlled patients are defined as patients with all items ≤ 1 in A and C category of GerdQ. (ITT, MITT and PP)	Summary statistics (number and percentage of patients in each category). Treatment group comparison of proportion of patients controlled, Fisher’s exact test.
Secondary Objective	Secondary variable	
To assess time to first relapse.	Time to first relapse, defined as the time to the patients first come to see the investigator because of symptom recur and need for treatment after 8 weeks or 2 weeks treatment in the two treatment regimen groups. (MITT and PP)	Median and percentiles of time to relapse, if appropriate. Treatment group comparison using Log-Rank test.
To assess symptom control rate after 8 /16 weeks visits in 24 weeks maintenance treatment/follow up period, as evaluated by GerdQ.	The symptom control rate after 8 and 16 weeks on-demand maintenance treatment/ follow up in the two different treatment regimen groups. Controlled patients are defined as patients with all items ≤ 1 in A and C category of GerdQ. (ITT, MITT and PP)	Summary statistics (number and percentage of patients in each category). Treatment group comparison of proportion of patients controlled, Fisher’s exact test.

Objective	Summary variables for analysis (including timepoint and population)	Statistical analysis methods or presentation of data
To assess the symptom relief rate after 8 weeks or 2 weeks esomeprazole treatment in the two different treatment regimen groups.	The symptom relief rate after 8 weeks or 2 weeks treatment in the two treatment regimen groups (Symptoms relief are defined as no more than one day with mild symptoms of GERD during the previous 7 days). (ITT)	Summary statistics (number and percentage of patients in each category).
In the 8 weeks treatment regimen group, to compare the symptom relief rate after 2 weeks and 8 weeks treatment	In the 8 weeks treatment regimen group, the symptom relief rate after 2 weeks and 8 weeks treatment (Symptoms relief are defined as no more than one day with mild symptoms of GERD during the previous 7 days). (ITT)	Summary statistics (number and percentage of patients in each category).
To compare the number of unscheduled hospital visit between the two different treatment regimen groups.	The number of unscheduled hospital visit in the two treatment regimen groups. (MITT and PP)	Descriptive statistics (number, mean, median, standard deviation, minimum and maximum). Treatment group comparison of unscheduled hospital visit, two sample t-test.
To measure patient satisfaction in the two different treatment regimen groups.	The proportion of patients satisfied (scores 1-4) or very satisfied (scores 1-2) in the two different treatment regimen groups after 8, 16 and 24 weeks on-demand maintenance treatment/ follow up. (MITT and PP)	Summary statistics (number and percentage of patients in each category). Treatment group comparison of proportion of patients satisfied and very satisfied, Fisher's Exact test.

Revised text:

Table 2 Efficacy objective and endpoints relating to objective

Objective	Summary variables for analysis (including timepoint and population)	Statistical analysis methods or presentation of data
Primary Objective	Primary variable	

Objective	Summary variables for analysis (including timepoint and population)	Statistical analysis methods or presentation of data
To compare the symptom control rate between 8 weeks esomeprazole treatment regimen group and 2 weeks esomeprazole treatment regimen group in co-diagnosed NERD and chronic gastritis patients, as evaluated by GerdQ after 24 weeks maintenance treatment/follow up.	The symptom control rate in 8 weeks treatment regimen group, compared with 2 weeks treatment regimen group after 24 weeks on-demand maintenance treatment/ follow up. Controlled patients are defined as patients with all items ≤ 1 in A and C category of GerdQ. (MITT and MITT-PP)	Summary statistics (number and percentage of patients in each category). Treatment group comparison of proportion of patients controlled, Fisher's exact test.
Secondary Objective	Secondary variable	
To compare the success rate between 8 weeks esomeprazole treatment regimen group and 2 weeks esomeprazole treatment regimen group in co-diagnosed NERD and chronic gastritis patients.	The success rate in 8 weeks treatment regimen group, compared with 2 weeks treatment regimen group after 24 weeks on-demand maintenance treatment/ follow up. Success is defined as patients who relieved after 8 weeks or 2 weeks esomeprazole treatment, and also get symptom controlled after 24 weeks maintenance treatment/follow up period. (ITT, ITT-PP)	Summary statistics (number and percentage of patients in each category). Treatment group comparison of proportion of patients succeeded, Fisher's exact test.
To assess time to first relapse.	Time to first relapse, defined as the time to the patients first come to see the investigator because of symptom recur and need for treatment after 8 weeks or 2 weeks treatment in the two treatment regimen groups. (MITT and MITT-PP)	Median and percentiles of time to relapse, if appropriate. Treatment group comparison using Log-Rank test.

Objective	Summary variables for analysis (including timepoint and population)	Statistical analysis methods or presentation of data
To assess symptom control rate after 8 /16 weeks visits in 24 weeks maintenance treatment/follow up period, as evaluated by GerdQ.	The symptom control rate after 8 and 16 weeks on-demand maintenance treatment/ follow up in the two different treatment regimen groups. Controlled patients are defined as patients with all items ≤ 1 in A and C category of GerdQ. (MITT and MITT-PP)	Summary statistics (number and percentage of patients in each category). Treatment group comparison of proportion of patients controlled, Fisher's exact test.
To assess the symptom relief rate after 8 weeks or 2 weeks esomeprazole treatment in the two different treatment regimen groups.	The symptom relief rate after 8 weeks or 2 weeks treatment in the two treatment regimen groups (Symptoms relief are defined as no more than one day with mild symptoms of GERD during the previous 7 days). (ITT,ITT- PP)	Summary statistics (number and percentage of patients in each category).
In the 8 weeks treatment regimen group, to compare the symptom relief rate after 2 weeks and 8 weeks treatment	In the 8 weeks treatment regimen group, the symptom relief rate after 2 weeks and 8 weeks treatment (Symptoms relief are defined as no more than one day with mild symptoms of GERD during the previous 7 days). (ITT, ITT-PP)	Summary statistics (number and percentage of patients in each category).
To compare the number of unscheduled hospital visit between the two different treatment regimen groups.	The number of unscheduled hospital visit in the two treatment regimen groups. (MITT and MITT-PP)	Descriptive statistics (number, mean, median, standard deviation, minimum and maximum). Treatment group comparison of unscheduled hospital visit, two sample t-test.

Objective	Summary variables for analysis (including timepoint and population)	Statistical analysis methods or presentation of data
To measure patient satisfaction in the two different treatment regimen groups.	The proportion of patients satisfied (scores 1-4) or very satisfied (scores 1-2) in the two different treatment regimen groups after 8, 16 and 24 weeks on-demand maintenance treatment/ follow up. Patient satisfaction will be measured 7-point scale (completely satisfied-1; very satisfied-2; quite satisfied-3; satisfied-4; dissatisfied-5; very dissatisfied-6; completely dissatisfied-7) (MITT and MITT-PP)	Summary statistics (number and percentage of patients in each category). Treatment group comparison of proportion of patients satisfied and very satisfied, Fisher's Exact test.

Reason for Amendment:

Relief rate is to evaluate the efficacy of initial 8 week or 2 week treatment, and symptom control rate is to evaluate the efficacy of 24 weeks maintenance treatment/follow up period. Now success rate is added to evaluate the efficacy of whole treatment regimen, it is the combination of relief and control.

Persons who initiated the Amendment:

Study physician

Section of protocol affected:

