12.2 Methods of statistical analyses

In general, the descriptive statistics (number, mean, median, standard deviation, minimum and maximum) will be performed for continuous variables. The frequency tables (number and percentage of subjects) will be performed for categorical variables. All statistical tests will be two-sided with the 5% level of significance.

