12.2.1 Analyses of efficacy endpoints

Analysis on efficacy endpoints will be performed for ITT, MITT and PP population.

Fisher's exact test will be used to assess statistical difference in symptom control rate in 8 weeks treatment regimen group, compared with 2 weeks treatment regimen group. Differences between treatment groups in the proportion of patients very satisfied (scores 1-2) and satisfied (scores 1-4) will also be analyzed using Fisher's exact test. Symptom relief after 8 weeks or 2 weeks treatment will be summarized with number and percentage of patients in each category.

The number of unscheduled hospital visit was compared between treatments using two-sample t-test. Kaplan-Meier method will be used to assess time to first relapse and a log-rank test to provide a comparison of treatment groups.

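### The objective to compare Week 2 and Week 8 relief within the 8-week arm is given only two percentages, which cannot show the precision of a change measured in the same patients

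*Protocol*

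**What the plan says.** Section 2.2, as revised by Amendment 1, lists this secondary objective: "In the 8 weeks treatment regimen group, to compare the symptom relief rate after 2 weeks and 8 weeks treatment". The revised efficacy table in section 6.3.1 repeats the verb: "to compare the symptom relief rate after 2 weeks and 8 weeks treatment". The variable in that row is "In the 8 weeks treatment regimen group, the symptom relief rate after 2 weeks and 8 weeks treatment", to be analysed in ITT and ITT-PP.

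The method column of the row reads "Summary statistics (number and percentage of patients in each category)" and nothing more. Section 12.2.1, which the amendment leaves unchanged, agrees: "Symptom relief after 8 weeks or 2 weeks treatment will be summarized with number and percentage of patients in each category". Revised section 6.3.2 defines relief as a proportion. None of these places names a difference, an interval, a cross-tabulation or a test for this objective.

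Two other rows of the same table show the contrast. The success-rate objective, also worded as a comparison, has "Treatment group comparison of proportion of patients succeeded, Fisher's exact test". The unscheduled-visit objective has "Treatment group comparison of unscheduled hospital visit, two sample t-test".

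**The concern.** The objective promises a comparison, but the method supplies two separate percentages. Both come from the same patients, so the uncertainty of the change depends on how many patients move from not relieved to relieved and how many move the other way. Neither percentage shows those counts. A reader of the report could see that one rate is higher than the other, but could not put a correct interval on the difference. Someone who applied the usual formula for two independent groups would generally get the wrong width.

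The objective is the protocol's planned look at whether relief in the 8-week arm is higher at Week 8 than it already was at Week 2. The Background says that one or two weeks of treatment can resolve reflux symptoms temporarily, so the question is relevant to the trial's argument, although it is secondary.

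**Working it through.** **Step 1. Objective against method, row by row (revised table, 6.3.1).**

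| Objective | Verb | Method beyond n and % |
|---|---|---|
| Symptom control at 24 weeks | compare | Fisher's exact test |
| Success rate | compare | Fisher's exact test |
| Time to first relapse | assess | log-rank test |
| Symptom control at 8 and 16 weeks | assess | Fisher's exact test |
| Relief after initial treatment, two arms | assess | none |
| Relief at Week 2 and Week 8, 8-week arm | compare | **none** |
| Unscheduled visits | compare | two-sample t-test |
| Satisfaction | measure | Fisher's exact test |

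Only one row is worded as a comparison and names no comparative method. The between-arm relief row is also descriptive, but its verb is consistent with that.

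**Step 2. Inputs for the illustration.** The protocol gives no figure for this objective to reproduce.
- n = 150: the approximate size of one arm (synopsis, target population).
- Week 8 relief 70%, or 105 of 150: an assumption, borrowed from the response rate in section 12.3, which carries no time point.
- Week 2 relief 60%, or 90 of 150: an assumption; the documents give no Week 2 rate.
- Two-sided 5% level (section 12.2).

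**Step 3. What the two percentages leave open.** Let b be the number who gain relief between the visits and c the number who lose it. The percentages fix only b − c = 105 − 90 = 15. At Week 8, 45 patients are not relieved, so c can be anything from 0 to 45.

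The exact two-sided McNemar p-value is min{1, 2·P(X ≤ c)}, with X binomial(b + c, ½). The 95% interval is 0.10 ± 1.96·√[(b + c) − (b − c)²/n]/n.

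| c lose | b gain | exact p | 95% interval (points) |
|---|---|---|---|
| 0 | 15 | 2 × (½)^15 = 0.00006 | 5.2 to 14.8 |
| 10 | 25 | 0.017 | 2.4 to 17.6 |
| 22 | 37 | 0.067 | 0.1 to 19.9 |
| 45 | 60 | 0.17 | −3.3 to 23.3 |

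All four rows would appear in the report as the same 60% and 70%.

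**Step 4. The independent-groups formula.** The half-width is 1.96·√(0.6·0.4/150 + 0.7·0.3/150) = 0.107, so the interval includes zero. The paired half-width depends on the split:
- 10% lose and 20% gain: 1.96·√[(0.30 − 0.01)/150] = 0.086.
- 5% lose and 15% gain: 1.96·√[(0.20 − 0.01)/150] = 0.070.
- No correlation between visits, so 0.6 × 0.3 = 18% lose and 0.4 × 0.7 = 28% gain: 1.96·√[(0.46 − 0.01)/150] = 0.107, equal to the independent result.

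**Step 5. Other Week 2 rates, with Week 8 held at 70%.** At 50%, p runs from below 0.0001 to 0.008. At 65% (98 of 150), it runs from 0.016 to 0.54. How much the missing counts matter to the conclusion therefore depends on the rates, but the interval width is undetermined in every case.

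**Step 6. Power.** For the first two splits in Step 4, the exact McNemar test with 150 patients has about 56% and 75% power.

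**The case against.** The strongest reply is that two rates from one arm, set side by side, are already a descriptive comparison and that the objective never promised a test. The other rows worded as comparisons are all between arms, so a lighter treatment of the only within-arm row may be deliberate. A paired interval is also the kind of detail a statistical analysis plan, not at hand here, may add. Part of this stands. It would be wrong to say that no comparison of any kind is made, or that none will be. It does not remove the point, because the protocol is not silent: its method column and section 12.2.1 both fix a descriptive method for an objective worded as a comparison. Amendment 1 revised the analysis populations in this row and left the mismatch in place.

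A reader might infer that the trial demonstrably collects the paired data. Table 1 does not show this. It has no row for symptom relief and ticks GerdQ only at Visit 1, and the GerdQ in Appendix C has no severity item, although relief is defined by days with mild symptoms. What can be said is that the stated variable requires relief at both visits, so the paired analysis asks for nothing beyond what that variable needs.

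A reader might also infer that a paired interval would exclude zero where an unpaired one would not. That follows only from chosen splits. With no correlation the two widths are equal, and other splits give an interval that includes zero.

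Finally, a reader might infer that the case for the 8-week regimen turns on this objective. It does not. A within-arm change has no concurrent control, so no test of it can separate continued treatment from natural course. The randomised comparisons of 24-week control and of success rate do have tests.

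**Conclusion.** The point holds as a mismatch on one secondary objective. The current text sets out to compare relief at two times in the same patients and fixes a method that cannot give the precision of that change. In the illustration, identical percentages fit exact p-values from 0.00006 to 0.17. That range rests on an assumed 150 patients, an assumed Week 2 rate and freely varied gains and losses; it shows what is undetermined and does not forecast a result.

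The importance is modest. The trial was not sized for this question, so the interval will say more than the p-value. The primary analysis and the sample size are unaffected.

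**What to change.** In the 6.3.1 row and in section 12.2.1, specify for the 8-week arm, in both ITT and ITT-PP:
- the 2×2 table of relief at Week 2 by relief at Week 8;
- the paired difference in proportions with a paired 95% confidence interval;
- McNemar's exact test (Fisher's exact test, used elsewhere for proportions, assumes independent groups and would not suit).

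Treat missing assessments the same way at both visits: for example, analyse patients with both assessments, with a sensitivity analysis that counts a missing assessment at either visit as not relieved. A rule applied to Week 8 alone would bias the change downward. With true rates of 60% and 70%, Week 2 complete and 10% of Week 8 values missing unrelated to outcome, the gain falls from 10 points to 0.70 × 0.90 − 0.60 = 3 points. With 15% missing it is 0.70 × 0.85 − 0.60 = −0.5 points.

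Describe the result as a within-arm change without a concurrent control, and list the relief assessment in Table 1 at both visits so that the schedule matches the variable.

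The cost is one extra table, a sentence or two of text and one more secondary test. If the team wants only a description, rewording the objective from comparing to describing would remove the inconsistency but leave the precision of the change unreported.
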